3.2.2 Secondary Endpoints

For mtDNA and nDNA subjects:

- Absolute values, changes from baseline, and incidence of potentially clinically significant changes in:
 - Laboratory safety tests
 - Electrocardiograms (ECG)
 - Supine vital signs
 - Eye assessments

For mtDNA subjects:

- Absolute values and changes from baseline in:

- Distance walked during the 12MWT*
- MFIS total scores and sub-scale scores*

Patient Global Impression of Severity (PGIS) scores for fatigue and muscle symptoms

- Brief pain inventory (BPI) pain severity and pain interference scores*
 - Patient Reported Outcomes Measurement Information System (PROMIS) Short Form- Functional Assessment of Chronic Illness Therapy (FACIT) Fatigue 13a scores*
 - 36-Item Short Form Health Survey (SF-36) domain scores (7-day recall)*
 - Work Productivity and Activity Impairment Questionnaire: Specific Health Problem (WPAI:SHP) scores*
 - First 6-minute walk distance and last 6-minute walk distance*
 - Phenotypic description questions*
- Patient Global Impression of Change (PGIC) scores for fatigue and muscle symptoms

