7.1.6 Eye Examination

All eye examinations should be carried out by an appropriately qualified professional. Best efforts should be made to ensure the same professional undertakes the slit lamp examinations for a particular subject in both the STRIDE study and in this long-term safety study. If the lens is clear, that should be recorded. If a cataract is identified, the cataract should be

classified and graded against the Lens Opacity Classification System III, ([Chylack et al, 1993](#)).

In addition, best corrected distance visual acuity (including refraction) should be assessed.

For scheduling reasons, the above assessments may be conducted \pm 14 days of the visit window given for the eye assessments.

In addition, any subject who experiences any visual symptoms during the study should have an additional eye examination as appropriate.

Eye examinations will not be repeated if within 6 months of a previous test within STRIDE.

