8.6 Safety Analyses

No imputation will be used for handling missing data, with the exception of conservative approaches taken for missing AE information (e.g., intensity). Details of such conventions will be documented in the SAP.

Treatment-emergent adverse events will be summarized by SOC and Preferred Term, in accordance with the MedDRA coding dictionary. The number of subjects reporting each AE preferred term will be tabulated for all TEAEs and separately for those considered as at least possibly related to study treatment by the Investigator. Number of subjects reporting SAEs and AESIs will also be tabulated.

Changes from baseline in laboratory parameters (including bone and calcium markers), vital signs, ECG and eye examinations data will be summarized by visit.

The incidence of potentially clinically significant laboratory and ECG values (e.g., increase in QTcF ≥ 30 msec from baseline or an absolute QTcF value of ≥ 500 msec).

Absolute values and changes from baseline for the DXA endpoints will be summarized. Summaries will be presented over all subjects and for the following demographic sub-groups:

- Men
- Pre-menopausal women
- Post-menopausal women

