3.2.2. Secondary Endpoints

- Absolute values, changes from Baseline and incidence of potentially clinically significant changes in:

- Laboratory safety tests
- Electrocardiograms (ECGs)
- Vital signs
- Eye assessments

For mtDNA-PMM subjects

- Absolute values and changes from Baseline in:
 - Distance walked during the 12-minute walk test (12MWT)*
 - Modified Fatigue Impact Scale (MFIS) Total scores and sub-scale scores*
 - Patient Global Impression of Severity (PGIS) score for fatigue and muscle symptoms
 - Brief Pain Inventory (BPI) pain severity and pain interference scores*
 - Patient-Reported Outcomes Measurement Information System (PROMIS) Short Form – Functional Assessment of Chronic Illness Therapy (FACIT) Fatigue 13a scores*
 - 36 Item Short Form Survey (SF-36) domain scores (7-day recall)*
 - Work Productivity and Activity Impairment questionnaire: Specific Health Problem (WPAI:SHP) scores*
 - First 6-minute walk distance and last 6-minute walk distance*
 - Phenotypic description questions
- Patient Global Impression of Change (PGIC) scores (muscle and fatigue symptoms)

**Collected up to Month 24 only.*

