3.5. DETERMINATION OF SAMPLE SIZE

The sample size for this study is not based on statistical justification. Recruitment of mtDNA-PMM subjects will be limited to those subjects who participated in REN001-201 or REN001-101, and reside in countries where this long-term safety study is approved. It is estimated that approximately 150 mtDNA-PMM subjects will be enrolled.

It is anticipated that up to 50 nDNA-PMM subjects may also be enrolled.

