6.7. EYE EXAMINATIONS

Eye examination data will be performed during the study by an appropriately qualified professional. Any abnormality considered clinically significant, will be reported as an AE.

To allow for scheduling of the eye examinations the REN001-201 Week 24 (Month 6) assessment can occur up to 14 days after the visit. Hence, this examination could occur after the start of administration of mavodelpar in REN001-202; this period is not considered sufficient time to have an impact on eye examination results. Therefore, for those mtDNA-PMM subjects who received placebo in REN001-201, enrolled in REN001-202 at REN001-201 Exit, enrol from study REN001-101 or for nDNA-PMM subjects this record will still be considered the baseline record relative to the start of mavodelpar provided it occurs within 14 days of the first dose of mavodelpar.

Baseline eye examinations will not be required for REN001-201 Exit subjects if the screening visit is within 6 months of the last REN001-201 examination.

Best corrected visual acuity (BCVA) can be assessed using the LogMAR scale, ETDRS letters or Snellen line. All results will be converted to the LogMAR scale before calculating changes from baseline at each visit for left and right eye BCVA (Roy 2003).

Where the Snellen scale has data recorded as x/y the MAR value is calculated by dividing y by x and then the LogMAR is the base 10 logarithm of the MAR value [i.e., $\text{LogMAR} = \log_{10}(\text{MAR})$]. Hence, higher scores indicate worse BCVA and increases from baseline indicate deterioration.

A change of 0.02 in LogMAR is equivalent to 1 letter. Hence, a Snellen scores with ‘-z’ or ‘+z’ indicating z letters fewer, or z letters more, respectively, will require an adjustment to the LogMAR score; 0.02 will be added or subtracted, respectively, for each letter (z).

e.g.,

$$20/15-1: \text{LogMAR} = \text{Log}_{10}(15 \text{ divided by } 20) + 0.02 = -0.105$$

$$20/15+1: \text{LogMAR} = \text{Log}_{10}(15 \text{ divided by } 20) - 0.02 = -0.145$$

If the Snellen scale is not reported in x/y format or x/y±z format, then the conversion to logMAR will not be done.

A change of 0.3 LogMAR (equivalent to 15 letters or 3-line change) is considered meaningful.

Refraction error based on spherical equivalent will be derived for each eye using the following formula:

$$\text{Spherical Equivalent (diopters)} = \text{cylinder (diopters)}/2 + \text{sphere (diopters)}$$

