8. GENERAL ASPECTS FOR STATISTICAL ANALYSIS

8.1. HYPOTHESIS TESTING

No formal statistical testing is planned.

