12.7. EYE EXAMINATION

Observed and change from baseline values for the 4 cataract gradings in LOCS III (nuclear opalescence, nuclear colour, cortical and posterior subcapsular cataracts) will be summarized by visit using descriptive statistics. The summary will be across both eyes (i.e., each subject will contribute 2 values if they have a left and right eye reading at the visit) and repeated for the worst change at each visit.

Eye examination data will be listed. Eye examination data will be listed separately - refraction, BCVA, pinhole visual acuity, slit lamp examination, cataract grading, tonometry and irido-corneal drainage angle assessment.

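### SAP 12.7 gives visual acuity and refraction no aggregate summary and plans no eye incidence table, although eye assessments are a secondary safety endpoint that the protocol says will be summarised by visit

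*SAP*

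**What the plan says.** Protocol 3.2.2 sets a secondary endpoint for mtDNA and nDNA subjects: "Absolute values, changes from baseline, and incidence of potentially clinically significant changes in" four items, namely laboratory tests, ECGs, supine vital signs and eye assessments. SAP 3.2.2 repeats it: "Absolute values, changes from Baseline and incidence of potentially clinically significant changes in" the same four.

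The eye examination is more than cataract grading. After the slit-lamp instructions, Protocol 7.1.6 adds: "In addition, best corrected distance visual acuity (including refraction) should be assessed".

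Protocol 8.6 commits to an analysis: "Changes from baseline in laboratory parameters (including bone and calcium markers), vital signs, ECG and eye examinations data will be summarized by visit". The protocol synopsis makes the same commitment and includes the absolute values.

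SAP 6.7 prepares for this. For visual acuity: "All results will be converted to the LogMAR scale before calculating changes from baseline at each visit for left and right eye BCVA". It gives Snellen conversion rules, sets 0.3 LogMAR as a meaningful change, and derives spherical equivalent with its change from baseline at each visit.

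The output section does not follow through. SAP 12.7 summarises the four LOCS III gradings by visit, across both eyes and for the worst change. The remaining measures go to listings: "Eye examination data will be listed separately - refraction, BCVA, pinhole visual acuity, slit lamp examination, cataract grading, tonometry" and the drainage-angle assessment. SAP 14, which should record departures from the protocol's analyses, records none.

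**The concern.** A secondary safety endpoint is defined, measured and derived, but two of its eye measures never reach a table. The incidence component has no eye table at all, not even for LOCS III.

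This matters because lens change is a named risk. Protocol 1.4.2.2 gives a rat cataract finding as the reason for eye examinations in REN001 trials and specifies visual acuity alongside the slit lamp. Refraction has also lost a route into the summaries: SAP 6.1 notes that a spherical-equivalent loss of 0.75 dioptres or more was an adverse event of special interest (AESI) under Protocol Versions 1.0 and 2.0, but is no longer routinely reported as one under Version 3.0.

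A clinical study report built to this SAP would leave the reader to work out from per-subject listings how acuity and refraction moved over 48 months, and how many subjects lost a meaningful amount of vision.

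**Working it through.** No power or error-rate figure bears on this. SAP 8.1 states "No formal statistical testing is planned" and SAP 3.5 states "The sample size for this study is not based on statistical justification". The check is a comparison of sections, with two small sums.

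**Step 1. Derived eye measures against planned output.**

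| Measure | Change derived in SAP 6.7 | Output in SAP 12.7 |
|---|---|---|
| BCVA (LogMAR) | Each visit, left and right eye | Listing only |
| Spherical equivalent | Each visit, per eye | Refraction listing only |
| LOCS III, four gradings | Yes, plus worst change across eyes | By-visit summary and listing |

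One of three measures is summarised.

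**Step 2. The four items of the same endpoint.**

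| Item | By-visit observed and change | Number of subjects crossing a limit |
|---|---|---|
| Laboratory (SAP 12.2) | Yes | Yes: CK, aldolase, troponin I, potential Hy's law |
| Vital signs (SAP 12.4) | Yes | Yes: blood-pressure change categories |
| ECG (SAP 12.5) | Yes | Yes: QTcF categories |
| Eye (SAP 12.7) | LOCS III only | None |

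The eye is the only item of the four with a partial by-visit summary and no incidence table.

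**Step 3. Is a threshold available?** SAP 6.7 equates one letter with 0.02 LogMAR and calls 15 letters meaningful. 15 × 0.02 = 0.30, which reproduces the SAP's 0.3 LogMAR. The limit is consistent and ready to use, but no planned output uses it.

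**Step 4. Does the LOCS III table stand in for the others?** Under Protocol 7.1.6 a clear lens is recorded as clear, and grading is called for when a cataract is identified. Neither SAP 6.7 nor SAP 12.7 says how a clear lens is scored. Read literally, subjects with clear lenses may have no LOCS III value, and a new cataract may have no graded baseline. Visual acuity carries no such condition.

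**Step 5. How much data is involved?** Protocol 6.3 to 6.13 schedule eye examinations at Months 3, 6, 12, 18, 24, 30, 36, 42 and 48, which is 9 visits. Planned enrolment is about 150 mtDNA plus up to 50 nDNA subjects, 200 in all. 9 visits × 2 eyes × 200 subjects = 3,600 post-baseline values per measure in REN001-202. This is a ceiling: it ignores withdrawal and missed visits, and SAP 6.7 does not convert Snellen results recorded outside its accepted formats.

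**The case against.** The strongest defence is that the information is not lost. SAP 8.2 puts changes from baseline in the listings, and refraction and BCVA each have one. SAP 6.7 makes any clinically significant eye abnormality an adverse event, so it reaches the SAP 12.1 tables. New or worsening cataract is an AESI with its own summary. Under Protocol 3.11 the Safety Review Committee sees eye examinations. All of this stands. A reader might infer that these measures have no result at all; the documents do not support that.

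Second, the protocol does not name the eye parameters to tabulate, Protocol 8 leaves detail to the SAP, and the stated eye risk is cataract, which SAP 12.7 does summarise. In addition, the incidence sentence in Protocol 8.6 mentions only laboratory and ECG values. This is partial mitigation. The endpoint definition in both documents covers eye assessments for all three components, and SAP 6.7 would have little reason to derive by-visit changes and set a meaningful difference if neither were to be reported.

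Two stronger readings are tempting and should not be made:

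- **That a refraction table is now the only systematic view of refractive shift.** The per-eye listing and the adverse-event route remain, and SAP 6.1 says only that such losses are not routinely AESIs any more.
- **That the missing table would reveal a shift of about one letter.** The documents give no standard deviation for LogMAR change. SAP 12 plans no confidence intervals for safety means. One letter is one-fifteenth of the SAP's own threshold. After the 24-week randomised phase there is no concurrent control to separate a small drift from ageing or disease.

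**Conclusion.** The gap is real and undeclared. Following the SAP as written, LogMAR BCVA and spherical equivalent have no aggregate summary, and the incidence part of the endpoint has no eye table. One of three derived eye measures is tabulated, and up to 3,600 values for each of the other two appear only in listings. Listings and investigator-judged adverse events are useful, but they are not the by-visit summary that the protocol commits to, and they do not readily show a gradual change across subjects.

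The consequence is limited. The primary adverse-event endpoints and the sample size are untouched, no test is affected, and the data remain available for later tabulation. It should be corrected before database lock, but it does not threaten the study's main conclusions.

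The conclusion rests on the text of the two documents. It assumes only that no acuity, refraction or eye-incidence table is specified elsewhere, for example in the separate table shells mentioned in SAP 2.1, which are not part of the documents. The remark on clear lenses in Step 4 depends on how the case report form records them, which is also not shown; the conclusion does not need it.

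**What to change.** Add to SAP 12.7, for each safety set and reporting group:

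- by-visit summaries of observed values and change from baseline for LogMAR BCVA and for spherical equivalent, for the left eye, the right eye and the worse-changing eye, using the SAP 8.2 descriptive statistics;
- the number and percentage of subjects whose BCVA worsens by at least 0.3 LogMAR from baseline. The on-treatment rule in SAP 12.2, at least one post-baseline value including unscheduled visits, would serve.

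State how the worse-changing eye is chosen. SAP 6.7 defines this only for LOCS III. For LogMAR it is the larger increase, since higher scores are worse; for spherical equivalent the direction has to be written down.

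The cost is a few tables from variables already derived, with no new data. If the sponsor prefers listings only, SAP 14 should say so and give the reason, but the endpoint would then remain without an aggregate result for these measures.

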12.8. COVID-19 EXPOSURE AND VACCINATION DATA

The following COVID-19 exposure and vaccination information will be summarized. The number (%) of subjects will be presented:

- Number of vaccination doses (0, 1, 2, 3, >4) received at each visit
- Documented COVID-19 prior to first dose and during the study

All data will be listed.

13. INTERIM ANALYSES

An interim synoptic CSR will be prepared for this study to be included in the regulatory submission package. The data cut will be the date of the last subject last visit in REN001-201 and the data will be extracted from the database after REN001-201 database has been locked. This CSR will include all REN001-202 data up to the data cut date and best efforts will be made to clean data up to this data cut date.

There will be a reduced set of safety outputs generated after submission for the 120-day safety update which is required as part of the submission package. The final CSR will occur after all subjects have had the ability to complete REN001-202, the data has been cleaned and the database locked.

An independently chaired Safety Review Committee (SRC) will review safety data at specified intervals for the duration of the study. The structure, function and operation of the SRC is detailed in the REN001-202 SRC charter. The SRC review of safety data will be limited to data from REN001-202 and will not be combined with REN001-201 data.

**14. CHANGES FROM PLANNED ANALYSES SPECIFIED
IN THE PROTOCOL**

None.

APPENDIX 1 – COUNTRY SPECIFIC PROTOCOL AMENDMENTS

The following country specific protocol amendments have been approved for REN001-202:

Country	Amendment, Version (Date)
France	Amendment 1, Version 1.0 (22nd December 2021)
Germany	Amendment 1, Version 1.0 (7th December 2021)
Netherlands	Amendment 1, Version 1.0 (12 July 2022)
Germany	Amendment 2, Version 2.0 (8 February 2023)
Netherlands	Amendment 2, Version 2.0 (1 February 2023)
Germany	Amendment 3, Version 3.0 (18 October 2023)

The following country specific protocol amendments have been approved for REN001-201:

Country	Amendment, Version (Date)
Canada	Amendment 3, Version 4.0 (21 st March 2021)
France	Amendment 3, Version 4.0 (1 st April 2021)
Germany	Amendment 3, Version 4.0 (20 th May 2021)
Canada	Amendment 4, Version 5.0 (29 th June 2022)
France	Amendment 4, Version 5.0 (29 th June 2022)
Germany	Amendment 4, Version 5.0 (29 th June 2022)

APPENDIX 2 – REN001-201 SCHEDULE OF ASSESSMENTS

Time and Events Table	Screening	Baseline ^{1,2} (Day 1)	Week 2 ³ (Day 14)	Week 4 ³ (Day 28)	Week 8 (Day 56)	Week 12 ^{2,4} (Day 84)	Week 16 (Day 112)	Week 18 ³ (Day 126)	Week 20 (Day 140)	Week 24 ^{2,4} (Day 168)	Early Termn ^{2,5}	Follow Up ³ (21-28 days post last dose)
Visit number	1	2	3	4	5	6	7	8				
Window (days)			±3	±3	±7	±7						
Informed Consent ²⁰	X											
Completion of Proforma and data entered into eCRF ⁶	X											
Demographics	X											
Medical/medication/drug/alcohol/tobacco history ⁷	X											
Physician completion of PMM phenotypic description		X								X	X	
Physical exam ⁸	X	X				X				X	X	
12-lead ECG	X	X				X				X	X	
Supine Vital signs (BP, PR and temperature)	X	X	X	X				X		X	X	X
Serum FSH ⁹	X											
HbA1c	X									X	X	
Hepatitis B/C/HIV	X											
Safety labs (inc. urinalysis)	X	X ¹⁰	X	X		X		X		X ¹¹	X	X ¹¹
Blood sample for bone and calcium markers		X				X				X	X	
Pregnancy Test (WOCBP only) ¹²	X	X		X	X	X	X		X	X	X	X
Blood sample for genotyping ¹³	X											
Population PK blood sample ¹⁴		X	X	X		X		X		X	X	
Urine drugs of abuse	X	X				X				X	X	

Time and Events Table	Screening	Baseline ^{1,2} (Day 1)	Week 2 ³ (Day 14)	Week 4 ³ (Day 28)	Week 8 (Day 56)	Week 12 ^{2,4} (Day 84)	Week 16 (Day 112)	Week 18 ³ (Day 126)	Week 20 (Day 140)	Week 24 ^{2,4} (Day 168)	Early Term ^{2,5}	Follow Up ³ (21-28 days post last dose)
Urine NTX		X				X				X	X	
Sites to provide appropriate snacks and lunch	X	X				X				X	X	
Pedometer eDiary data collection (inc. review)	X	X ¹⁵	X			X		X		X		
MFIS / PGIS (muscle symptoms), PGIS (fatigue symptoms) and PROMIS – Short form FACIT fatigue 13a	X	X	X			X		X		X	X	
SF-36 / BPI and WPAI:SHP		X	X			X		X		X	X	
PGIC (muscle symptoms) and PGIC (fatigue symptoms)										X	X	
12 Minute Walk Test	X ¹⁶	X				X				X	X	
30STS		X				X				X	X	
IMP Capsule Counts			X	X		X		X		X	X	
Eye examination	X ¹⁷					X				X	X	
Wrist radiograph	X ¹⁸											
DXA Scan (REN001-201-DXA sub-study) ²¹	X									X	X	
Concomitant medication review	X											X
Dosing		X ¹⁹									X	
AE collection and reporting	X											X

1. Screening visit must take place a maximum of 8 weeks before the Baseline visit.
2. If appropriate and feasible Baseline, Week 12, Week 24 /Early Termination visits may be conducted over 2 days at the Investigators discretion.
3. In countries where the regulatory body allows, visit may be in the Study Center or a home nursing visit.
4. Only review of concomitant medications, AE's MFIS and 12MWT will be conducted if the subject has discontinued from study drug treatment but has not withdrawn from the study. If the subjects had an ET visit within 2 weeks of either of these a visit is not required.

5. As a minimum, subjects should have review of concomitant medication and AE's, vital signs (including temperature), complete questionnaires, safety laboratory blood (including HbA1c, bone and calcium markers and PK analysis) and urinalysis (including pregnancy tests for WOCBP, drugs of abuse and NTX) and IMP capsule counts.
6. Patient Screen Oversight Committee will review Proforma data and give a decision or request more information within 7 working days.
7. Subjects will be excluded from the study at the Investigators discretion for alcohol and/or drug dependency. Use of opiates/cannabis for medical reasons is acceptable with prescription evidence or at the Investigators discretion.
8. Full physical exam, height and weight at Screening; full physical exam and weight at Baseline; brief, symptom-directed physical exam and weight only at Weeks 12 and 24.
9. Serum FSH testing for post-menopausal females 45 years and older. Serum FSH test must be performed for all women who participate in the REN001-201-DXA sub-study who have not already had an FSH test as part of the parent REN001-201 study.
10. An additional 10 mL blood sample will be taken pre-dose at baseline and the serum will be stored frozen at the central laboratory as a reference sample in the event that re-analysis of protocol stated tests are required.
11. If any clinically significant abnormalities are noted at the Week 24 visit, these should be followed up until resolved.
12. WOCBP will be supplied with urine home pregnancy test kits at Study Center visits to test at Weeks 8, 16 and 20. The Study Center must contact the subject to confirm the pregnancy test result in a timely manner.
13. Blood sample for local genotype testing will only be conducted with prior Sponsor approval and definitive results must be available prior to the Baseline visit.
14. At the Baseline, Week 12 and Week 24 visits, blood samples will be taken pre-dose and then at 1, 2, 3, and 4 hours post-dose. On the other visits, a single sample can be taken at any time post-dose provided the dosing date and time are recorded.
15. Review of Screening (pre-treatment) pedometer data at Baseline.
16. Screening 12MWT must be at least 4 weeks before the Baseline 12MWT.
17. The Screening eye examination can be performed at any time between the initial Screening and Baseline Visit for scheduling reasons.
18. Subjects <25 years old only.
19. Dosing on Baseline, Week 12 and Week 24 visits should be under the supervision of the site staff.
20. A separate informed consent will be required for the REN001-201-DXA sub-study.
21. Only conducted at sites, on eligible subjects, which are participating in the REN001-201-DXA sub-study. The screening DXA scan should be performed no more than 8 weeks prior to the start of dosing. If a subject discontinues study treatment after at least 20 weeks in the study they will be asked to have a follow-up, scan within 4 weeks of their last dose of study treatment.
